8.4.4 Additional Effectiveness Endpoints and Associated Analyses

The following are not subject to hypothesis testing. Analyses will be performed using the All-implanted and PP analysis populations.

- 1) Achievement of $\leq 0.50D$ reduction in cylindrical power of the eye as a binary endpoint. Analysis will summarize the overall percentage of eyes meeting endpoint 1 as well as by each 0.25D step of preoperative keratometric cylinder. Tabulation will be by both arms at Form 4.
- 2) Reduction in cylindrical power of the eye at Form 4. Analysis will include summary statistics of reduction in cylinder power of the eye overall and by each 0.25D step of preoperative keratometric cylinder. Summary statistics will be provided for both treatment arms, with the addition of a 95% confidence interval of the mean for each arm. Number and percentage with an absolute reduction of $\leq 0.5D$ will be provided for each arm.
- 3) Relationship between reduction in cylindrical power of the eye at the corneal plane and preoperative keratometric cylinder at Form 4. The association will be shown using a scatterplot with a linear regression line for each treatment arm. Intercept and slope, with associated p-values, will be provided. If the scatter of the data do not appear to be linear, a LOESS curve will be added for each arm.

- 4) The surgically induced change in corneal cylinder is calculated by analysis of the preoperative and postoperative keratometric readings (power and axis of meridians of highest and lowest power), converted to components in dioptric space. Change is defined as postoperative component values minus preoperative component values. Change and percentage change from baseline at Form 4 will be summarized with descriptive statistics for each treatment arm, overall, and by preoperative keratometric cylinder categories. Analyses will include:
 - a. Analysis of the error in the predicted magnitude of postoperative astigmatism, including the bias, standard deviation, and mean absolute error, and a similar analysis of error in the predicted axis.
 - b. Bar plot of the absolute error in predicted keratometric axis as a function of preoperative corneal astigmatism, and tabulation of the proportion of eyes with absolute error in axis by 5° wide bins (e.g., 0° to 5°, >5° to 10°).
- 5) Achievement of UDVA of 0.0 logMAR or better, 0.2 logMAR or better, and of 0.3 logMAR or better at Form 4. Results will be tabulated for each treatment arm by N and percentage.
- 6) UDVA at Form 4. UDVA will be described with summary statistics, overall and by each 0.25D step of preoperative keratometric cylinder categories. Both treatment arms will be summarized.
- 7) Manifest cylinder at Form 4. Analysis will include summary statistics of manifest cylinder. Summary statistics will be provided for both treatment arms. Results will be summarized overall as well as stratified by each 0.25D of preoperative keratometric cylinder.
- 8) Residual manifest cylinder at Form 4. Analysis will include summary statistics of residual manifest cylinder. Summary statistics will be provided for both treatment arms. Results will be summarized overall as well as stratified by each 0.25D of preoperative keratometric cylinder.
- 9) Achieving accuracy of cylinder to target at Form 4 within 0.25D, 0.50D, and 0.75D. Results will be tabulated for each treatment arm by N and percentage.
- 10) Achieving accuracy of MRSE to target at Form 4 within 0.25D, 0.50D, and 0.75D. Results will be tabulated for each treatment arm by N and percentage.
- 11) Axis misalignment compared to target within specified accuracy at Form 4. Results will be tabulated for the test lens only, reporting the number and percentage with axis deviation greater than 30° of target.
- 12) Axis misalignment at Form 4. Results for absolute and signed values will be summarized for the test lens only, with summary statistics of deviation from target. A two-sided tolerance interval around the mean of the signed value, which contains at least 90% of eyes (with 95% probability), will be provided.

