#### Postoperative Adverse Events

- Anterior uveitis (including iritis and iridocyclitis)
- Capsular block syndrome
- Choroidal detachment/hemorrhage
- Chronic anterior uveitis [anterior segment inflammation characterized by grade 1+ cell or greater (using the Standardization of Uveitis Nomenclature [SUN] criteria) that is persistent for greater than 3 months after surgery, or relapses in less than 3 months after discontinuation of therapy, or the subject is maintained on therapy for more than 3 months to control inflammation.] Note that any iritis present at the final visit is considered significant and should be counted as a 'persistent ISO SPE event'.
- Visually significant corneal edema [corneal swelling (stromal or epithelial) resulting in BCDVA of 0.3 logMAR or worse at Form 3 or later]. Note that any corneal stromal edema present at the final visit is considered significant and should be counted as a 'persistent ISO SPE event'.
- Clinically significant cystoid macular edema (CME) diagnosed by clinical exam and adjunct testing (e.g., OCT or other method), resulting in BCDVA of  $\leq 0.3$  logMAR at Form 3 or later
- Endophthalmitis (intraocular inflammation leading to diagnostic vitreous tap and use of intraocular antibiotics)
- Flat anterior chamber with lens/cornea touch or a shallow chamber with iridocorneal apposition without lens/cornea touch
- Anterior Capsular Contraction Syndrome (ACCS, Phimosis)
- Hypopyon
- Corneal endothelial damage
- Incorrect IOL power resulting in secondary surgical intervention
- Increased IOP (elevation of IOP  $\geq 10$  mmHg above the IOP measured at the Preoperative Visit to a minimum of 25 mmHg)
- Infectious keratitis
- IOL damage resulting in secondary surgical intervention

- IOL dislocation, tilt, decentration, luxation, rotation resulting in secondary surgical intervention
- Best-corrected distance visual acuity loss of 2 lines (10 letters) or more on the ETDRS chart measured at or after postoperative Form 4 compared to any prior postoperative visit
- Best-corrected distance visual acuity loss of 2 lines (10 letters) or more since the prior visit
- Mechanical pupillary block (A shallowing of the anterior chamber due to obstruction of aqueous humor flow from the posterior to anterior chamber through the pupil by the crystalline lens, vitreous face, or implanted device)

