#### 9.11 ADDITIONAL ENDPOINTS AND ASSOCIATED ANALYSES

The following are not subject to hypothesis testing.

- 1) Achievement of  $\leq 0.50$  D reduction in cylindrical power of the eye as a binary endpoint. Analysis will summarize the overall percentage of eyes meeting endpoint 1 as well as by each 0.25 D step of preoperative keratometric cylinder. Tabulation will be by both arms at Form 4.
- 2) Reduction in cylindrical power of the eye at Form 4. Analysis will include summary statistics of reduction in cylinder power of the eye overall and by each 0.25 D step of preoperative keratometric cylinder. Summary statistics will be provided for both treatment arms, with the addition of a 95% confidence interval of the mean for each arm. Number and percentage with an absolute reduction of  $\leq 0.5$  D will be provided for each arm.
- 3) Relationship between reduction in cylindrical power of the eye at the corneal plane and preoperative keratometric cylinder at Form 4. The association will be shown using a scatterplot with a linear regression line for each treatment arm. Intercept and slope, with associated p-values, will be provided. If the scatter of the data do not appear to be linear, a LOESS curve will be added for each arm.
- 4) The surgically induced change in corneal cylinder is calculated by analysis of the preoperative and postoperative keratometric readings (power and axis of meridians of highest and lowest power), converted to components in dioptric space. Change is defined as postoperative component values minus preoperative component values. Change and percentage change from baseline at Form 4 will be summarized with descriptive statistics for each treatment arm, overall, and by preoperative keratometric cylinder categories. Analyses will include:
  - a) Analysis of the error in the predicted magnitude of postoperative astigmatism, including the bias, standard deviation, and mean absolute error, and a similar analysis of error in the predicted axis;

- b) Bar plot of the absolute error in predicted keratometric axis as a function of preoperative corneal astigmatism, and tabulation of the proportion of eyes with absolute error in axis by 5° wide bins (e.g., 0° to 5°, >5° to 10°).
- 5) Achievement of UCDVA of 0.0 logMAR or better, 0.2 logMAR or better, and of 0.3 logMAR or better at Form 4. Results will be tabulated for each treatment arm by N and percentage.

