8.7.2 Stratification Analysis

Specific endpoint values at Form 4 will be stratified by preoperative keratometric cylinder. These include reduction of 0.5D cylindrical power as a binary endpoint, absolute reduction in cylindrical power, logMAR UDVA, and manifest refractive cylinder. Additional stratifications will be by age (per section 8.1 categorization), race, and ethnicity.

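### The descriptive binary cylinder endpoint is inverted: eyes with little or no cylinder reduction meet it, and eyes with the full toric correction do not

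*SAP*

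**What the plan says.** **Cylinder, item 1.** SAP 8.4.4 lists as its first additional endpoint the achievement of a "\leq 0.50D$ reduction in cylindrical power of the eye as a binary endpoint". Protocol 9.11 item 1 carries the same inequality and continues "Analysis will summarize the overall percentage of eyes meeting endpoint 1", overall and by each 0.25 D step of preoperative keratometric cylinder, for both arms at Form 4.

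**Cylinder, item 2.** Both documents then ask for summary statistics of the reduction and add "Number and percentage with an absolute reduction of" 0.5 D or less, for each arm.

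**Cylinder, stratification.** SAP 8.7.2 names the endpoint again as "reduction of 0.5D cylindrical power as a binary endpoint", with no inequality at all.

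**Status.** Both lists state that these items are not hypothesis tested. SAP 8.1 adds that additional analyses should not support claims.

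**Macular edema.** The postoperative list in protocol 8.7.7 describes clinically significant CME as diagnosed by examination and "adjunct testing (e.g., OCT or other method), resulting in BCDVA of" 0.3 logMAR or less, at Form 3 or later. The corneal edema bullet just above it reads "resulting in BCDVA of 0.3 logMAR or worse at Form 3 or later".

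**The concern.** Item 1 speaks of achieving and meeting an endpoint, so it scores success. Yet success is defined as a small reduction. That contradicts the trial's stated direction of benefit: co-primary performance goal 1 is a smaller residual manifest cylinder in the toric arm, by 0.4 D or more, and the background section says non-toric lenses do not address astigmatism.

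The inequality appears in items 1 and 2 of both documents, so a text-extraction fault is unlikely. SAP section 2 says its methods supersede the protocol's. A programmer who follows SAP 8.4.4 would therefore produce a pivotal-study table, overall and by 0.25 D step, in which the control lens outperforms the toric lens. Reversing the sign after unmasking would look post hoc.

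The CME bullet raises a similar question of direction. Lower logMAR is better vision, so as worded the event is clinically significant when acuity is 20/40 or better.

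**Working it through.** **1. Direction of the acuity scale.** The Snellen denominator is 20 × 10^logMAR.
- 0.3 logMAR: 20 × 10^0.3 = 39.9, which reproduces the 20/40 given in protocol 8.7.7.
- 0.2 logMAR: 20 × 10^0.2 = 31.7, which reproduces the 20/32 in inclusion criterion 9.

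Lower logMAR is better, so 0.3 logMAR or less means 20/40 or better.

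**2. Single eyes under item 1.** Let R be preoperative minus postoperative cylinder.

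| R (D) | As written (R ≤ 0.50) | Reversed (R ≥ 0.50) |
|---|---|---|
| −0.25 (cylinder increased) | meets | fails |
| 0 | meets | fails |
| 0.50 | meets | meets |
| 1.03 | fails | meets |

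The 1.03 D is the corneal-plane cylinder in protocol Table 1.

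**3. Proportions by arm.** Take R as normal, so P(R ≤ 0.50) = Φ((0.50 − μ)/σ). Inputs:
- Toric μ = 1.03 D, from protocol Table 1.
- Control μ = 0 D, assumed because the lens has no toric correction.
- σ is not in the visible text; 0.2 to 0.5 D is assumed.

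At σ = 0.3, toric is Φ(−0.53/0.3) = Φ(−1.77) = 0.039 and control is Φ(0.50/0.3) = Φ(1.67) = 0.952.

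| σ (D) | Toric, as written | Control, as written | Toric, R ≥ 0.50 | Control, R ≥ 0.50 |
|---|---|---|---|---|
| 0.2 | 0.4% | 99.4% | 99.6% | 0.6% |
| 0.3 | 3.9% | 95.2% | 96.1% | 4.8% |
| 0.4 | 9.3% | 89.4% | 90.7% | 10.6% |
| 0.5 | 14.5% | 84.1% | 85.5% | 15.9% |

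**4. Sensitivity to the model.**
- Less favourable means (toric 0.75 D, control 0.1 D, both assumed), σ from 0.2 to 0.5 D: as written, toric 10.6% to 30.9% and control 97.7% to 78.8%.
- Vector model: preoperative cylinder c uniform on 0.75 to 1.50 D (the eligibility range), an aligned 1.03 D correction in the toric arm, independent normal error on each of two components, and R equal to c minus the length of the residual vector. At component SDs of 0.2, 0.3 and 0.4 D, toric is about 11%, 24% and 39% as written, and control about 99.6%, 97% and 94%.

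The vector model gives higher toric percentages partly because low-cylinder eyes are overcorrected. At c = 0.75 D the residual is 1.03 − 0.75 = 0.28 D, so R = 0.75 − 0.28 = 0.47 D even with perfect alignment. The order of the arms is the same in every case.

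**5. Reach of the CME wording.**
- As worded, CME leaving 0.5 logMAR (20 × 10^0.5 = 63, about 20/63) falls outside the bullet, and CME leaving 0.0 logMAR (20/20) falls inside it. An eye at exactly 0.3 logMAR satisfies both directions.
- Protocol 8.7.2.1 (cumulative events) and 8.7.2.2 (persistent events) list CME with no acuity qualifier. The comparison with ISO safety and performance endpoint (SPE) rates uses these categories.
- Protocol 8.7.5 requires every adverse event to be recorded.
- The 8.7.7 list is of anticipated events and is stated not to be exhaustive. Protocol 9.9 tabulates events by whether they were anticipated, so labelling is where the bullet could act.

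**The case against.** **The cylinder item has limited consequence.** This stands. The item is descriptive and barred from supporting claims. Item 2 already gives the mean reduction with a 95% confidence interval by arm, and residual cylinder and accuracy to target are tabulated separately. The percentage as written is nearly the complement of the reversed one, apart from eyes at exactly 0.50 D, so an alert reader could recover it. A reader might infer that the effectiveness conclusion is at risk. It is not: the co-primary tests and the stated 91% power do not use this item.

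**SAP 8.7.2 does not settle the intended criterion.** This stands too. It is tempting to read that section as proof that a reduction of at least 0.50 D was meant, but it gives no direction. A reduction within 0.50 D of the intended one, or a residual cylinder of at most 0.50 D, is also possible, and the co-primary definitions that might help are redacted.

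**Item 2 is not the same error.** Read alone, it is a neutral count of small reductions and does not score success. It needs aligning only because it shares the threshold with item 1.

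**The CME bullet does not hide cases.** A reader might infer that eyes losing vision to macular edema go uncounted. The documents do not support that. Such eyes are recorded as adverse events and enter the unqualified CME categories, and SAP 8.5.2 separately tabulates loss of 10 letters or more of best-corrected acuity.

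None of this rescues item 1. Its wording scores success, and the direction is wrong for a toric lens.

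**Conclusion.** The point holds for item 1 in both documents: the success criterion is inverted, and the by-arm table produced from it would favour the control. Under the normal model with assumed SDs of 0.2 to 0.5 D, the gap as written runs from 99.4% control against 0.4% toric to 84.1% against 14.5%. Other assumptions move the toric figure considerably, up to about 39% in the vector model, so no single percentage should be relied on; only the reversal is robust. The effect is confined to descriptive tables and the matching stratification. It is worth correcting because those tables belong to a pivotal study and the correction is free before unmasking.

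The CME wording is a separate and lesser inconsistency. It could affect how an event is labelled against the anticipated list, but not whether it is recorded or counted against the ISO rate.

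**What to change.** Before unmasking:

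1. Correct the direction of item 1 in protocol 9.11 and SAP 8.4.4. The most natural reading is a reduction of at least 0.50 D. If the sponsor meant a reduction within 0.50 D of the intended one, or a residual cylinder of at most 0.50 D, it should say so and define the endpoint that way.
2. Align the item 2 count in both documents with that choice, or label it explicitly as a count of small reductions.
3. Give the endpoint in SAP 8.7.2 the same direction and wording.
4. Separately, have the sponsor reconcile the acuity criteria in the CME and corneal edema bullets of protocol 8.7.7. The criterion itself is for the sponsor to set.

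The cost is a few words in four sections. No data collection, sample size or co-primary analysis changes.

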6.2 STUDY POPULATION

The subject population will consist of subjects with a diagnosis of cataract with pre-existing corneal astigmatism, eligible for phacoemulsification surgery followed by IOL implantation. Eligibility for the study will be determined at the preoperative visit. If the subject gives informed consent, the subject is enrolled.

Subjects will be enrolled at up to 10 investigational sites. Investigators will be encouraged to perform cataract surgery/IOL implant for at least 20 subjects per site; no Investigator may implant more than 25% of the total number of subjects planned. Site enrollment will be closely monitored to facilitate achievement of the stated enrollment goals and an even distribution across all sites.

To allow for approximately [REDACTED] and attrition between enrolment and randomization, a total of 300 subjects will be enrolled to ensure 230 subjects, 115 test and 115 control, will be implanted. It is anticipated that 13% of the 230 subjects will not complete the study, resulting in 200 with data at the Form 4 visit.

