6.3 INCLUSION CRITERIA

Eligible subjects must meet all the following inclusion criteria to be eligible for study participation:

1. Male or female adults, age 22 years or older at the Preoperative Visit.
2. Clinically significant cataract in the study eye eligible for standard phacoemulsification cataract surgery.
3. Eligible for receipt of an IOL power within the range of the investigational IOL in the study eye. **(The Investigational IOL is available in powers from +15 D to +30 D Spherical Equivalent)**
4. Pre-operative corneal astigmatism in the range: ≥ 0.75 D and ≤ 1.50 D in the study eye
6. Clear intraocular media other than cataract in the study eye.
7. Best corrected visual acuity equal to or worse than 0.3 logMAR, with or without a glare source in the study eye.
8. Ability to dilate pupil sufficiently (greater than or equal to 6.0 mm) to allow visualization of Toric IOL axis markings post-implantation in the study eye.
9. Projected BCDVA of 0.2 logMAR (20/32 Snellen) or better in the study eye after cataract surgery/IOL implantation as determined by the medical judgment of the Investigator.
10. Contact lens users must be willing to discontinue wear of their lenses in the study eye in accordance with the following requirements:
 - i. Rigid gas permeable and toric lenses for ≥ 7 days prior to the Preoperative Visit
 - ii. Soft non-toric contact lenses for ≥ 3 days prior to the Preoperative Visit
 - iii. All contact lens wearers must demonstrate a stable refraction within ± 0.50 D MRSE and 15 degrees astigmatic axis on two consecutive examinations at least 1 week apart in an eye to be treated.
11. Provide signed written consent prior to participation in any study-related procedures.
12. Ability, comprehension, and willingness to follow study instructions, and to complete all study visits.
13. Female subjects must be 1-year postmenopausal, surgically sterilized, or, if of childbearing potential, have a negative urine pregnancy test at the Preoperative Visit. Women of childbearing potential must use an acceptable form of contraception throughout the study. Acceptable methods include at least one of the following: intrauterine (intrauterine device), hormonal (oral, injection, patch, implant, ring), barrier with spermicide (condom, diaphragm), or abstinence.

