8 DATA ANALYSIS METHODS

8.1 DATA AND ANALYSIS CONVENTIONS

The following are some basic stipulations that, unless otherwise stated, apply by default throughout the plan.

- For the co-primary endpoints, the six-month postoperative visit (Form 4) will be the primary analysis time point unless otherwise noted. For the primary safety endpoints, the Form 4 visit will be the primary analysis time point.
- Monocular safety and effectiveness analyses will compare the test group and the control group.

- For all visual acuity-related endpoints in the study, best corrected distance visual acuity (BCDVA) and uncorrected distance visual acuity (UCDVA) are measured at 4 m using a ETDRS chart under photopic conditions. All postoperatively measured visual acuities are recorded and analyzed in logMAR for all endpoint analyses, summary statistics and calculations, and may be converted to Snellen equivalent values for tables, listings, and graphs.
- Safety data will not be imputed, although incomplete or missing dates may be imputed.
- Partial dates will be imputed for safety and effectiveness data, using the most conservative approach available; for safety data, dates will be imputed to result in the longest possible duration of a given adverse event; for effectiveness data, dates will be imputed to maximize the number of study days from the operative date.
- Partial dates in other contexts (e.g., medical history) will be imputed in a way to allow reasonable interpretation, such as to replace the missing date or the missing month with “1.” For example, a partial date recorded as “(missing date)/(missing month)/2020” will be imputed as “1/1/2020” and will be noted as “imputed” on any line listing.
- The expression “summary statistics” indicates sample size (N), mean, standard deviation (SD), median, minimum (Min), and maximum (Max) as applied to continuous variables, and indicates sample size (N), frequency and percent of relevant total as applied to categorical and some ordinal variables.
- All co-primary effectiveness and safety endpoints have to be met to claim overall effectiveness and safety success. Additional analyses and supportive analyses should not be used for the purpose of claims. Under this plan, type 1 error rates will be controlled at a significance level of 0.05 per individual hypothesis without adjustment for multiplicity.
- Data will be pooled across sites for overall analyses unless contraindicated by the poolability analysis in Section 7.8.1.

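### Percentage change from baseline for surgically induced corneal cylinder is, as written, a ratio to a signed vector component, so its mean, SD, minimum and maximum are unstable

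*SAP*

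**What the plan says.** Item 4 of SAP 8.4.4 and item 4 of Protocol 9.11 describe the same analysis in three steps.

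- Keratometry from before and after surgery (power and axis of both principal meridians) is "converted to components in dioptric space", which makes the components the quantity analyzed.
- The definition that follows works on those components alone: "Change is defined as postoperative component values minus preoperative component values". No change in cylinder magnitude is defined.
- The planned output is then set out: "Change and percentage change from baseline at Form 4 will be summarized with descriptive statistics for each treatment arm". The table is produced for all eyes together and again within bands of preoperative cylinder.

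SAP 8.1 defines summary statistics as N, "mean, standard deviation (SD), median, minimum (Min), and maximum (Max) as applied to continuous variables". Neither document names the components, gives another denominator for the percentage, or provides a rule for zero, near-zero or negative baselines.

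The relevant eligibility criterion is "Pre-operative corneal astigmatism in the range: ≥ 0.75 D and ≤ 1.50 D in the study eye". It limits the magnitude of the cylinder. No legible criterion limits its axis.

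SAP 8.4.4 introduces its list with "The following are not subject to hypothesis testing", and SAP 8.1 says that additional and supportive analyses are not to be used for claims.

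**The concern.** A percentage change is informative when the baseline is positive and well away from zero. Cylinder magnitude meets that condition in eligible eyes, but its vector components do not. They depend on the axis, take both signs, and pass through zero within the permitted range of magnitudes.

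The only change that item 4 defines is the component change, so a programmer following the text would divide by the preoperative component. The resulting column could show a large mean change in either direction when surgery had on average changed nothing, and one or two eyes could determine it. The breakdown by cylinder category makes this more likely, because the cells are smaller.

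**Working it through.** The plan gives no figure for this item, so there is nothing to reproduce. The check is algebra, followed by an illustration on stated assumptions.

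**Algebra (no distributional assumption).** The plan does not name its components. Using the usual double-angle form for cylinder C at axis a:

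- x = C·cos(2a), y = C·sin(2a)
- percentage change in x = 100·(post − pre)/pre

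For C = 1.00 D and a change of +0.25 D in x:

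| Axis | Preoperative x (D) | Percentage change |
|---|---|---|
| 180° | 1.00 | +25% |
| 90° | -1.00 | -25% |
| 46° | -0.0349 | about -716% |
| 45° | 0 | undefined |

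For C = 0.75 D at 44°, preoperative x is 0.0262 D and the same change gives about +955%. The y component behaves in the same way near 90° and 180°, where it is zero. One surgical effect thus yields either sign and almost any size, depending only on the preoperative axis.

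**How often baselines are small.** Inputs: C uniform on 0.75 to 1.50 D (range from eligibility, shape assumed); axis uniform (assumed). For small c, P(|x| < c) ≈ (2/π)·c·E(1/C), and E(1/C) = ln(1.50/0.75)/0.75 = 0.924. With c = 0.10 D this is 0.637 × 0.10 × 0.924 = 0.059, so about 6% of baselines lie within 0.10 D of zero. By symmetry half are negative.

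**Effect on the mean.** Adding an assumed component change with mean 0 and SD 0.30 D, simulated samples of 100 eyes gave a 95% range for the mean percentage change of roughly -290% to +270%. The underlying distribution is symmetric about zero, so the unequal limits reflect simulation error. Because the baseline has positive density at zero, the ratio has no finite expectation, and a larger sample would not settle the mean.

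**Sensitivity to the assumptions.** The next runs used arms of 115 eyes, from "230 subjects, 115 test and 115 control, will be implanted". The assumed SD was varied from 0.2 to 0.4 D, and axes were either uniform or concentrated near 90° and 180°. True mean change was zero throughout.

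| Case | 95% range of the arm mean | Median SD |
|---|---|---|
| Mildest: x, concentrated axes, SD 0.2 D | -46% to +37% | 48% |
| Most severe: y, concentrated axes, SD 0.4 D | -847% to +694% | 819% |

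**Exact zeros.** These need an axis recorded on a multiple of 45°. If axes are recorded in whole degrees and spread uniformly (both assumed), 2 of 180 values give x = 0. The SAP expects 200 eyes with Form 4 data, or about 100 per arm. The chance of at least one zero x baseline in an arm is then 1 − (178/180)^100 = 0.67.

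**The alternative denominator.** Percentage change in cylinder magnitude, under the same assumptions, has a per-eye SD of about 19% to 36%. With uniform axes, the mean of an arm of 115 has a 95% range of -1.4% to 5.2% (SD 0.2 D) or 1.1% to 14.0% (SD 0.4 D).

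**The case against.** The strongest reply is that the authors meant percentage change in cylinder magnitude. The item concerns change in corneal cylinder and is broken down by cylinder magnitude, so this is plausible. Neither document says it, however, and under SAP section 2 the SAP's methods supersede the protocol's, so the literal text would be programmed.

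The other objections limit the point, and these stand:

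- **Non-definition is the exception.** A reader might infer that the whole summary is undefined. That holds only for an eye with a component of exactly zero. Otherwise the defect is instability and sign reversal.
- **The median is steadier.** Under the uniform-axis assumptions above, the median of 100 eyes stays within about ±10%. It still mixes values whose sign depends on the baseline.
- **The rest of item 4 is sound.** A reader might infer that the account of surgically induced change, or of error in predicted astigmatism, is compromised. The component change in diopters is valid, and the prediction-error and axis analyses in 4a and 4b do not use the percentage. Nothing in the documents makes the reading of residual cylinder depend on this column.
- **No claim depends on it.** The item is descriptive and excluded from claims.

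Inclusion criterion 5 is not legible, so an axis restriction cannot be ruled out. To remove the problem for both components, it would have to exclude eyes near every multiple of 45°.

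**Conclusion.** The point holds as a minor specification error. Taken literally, both documents plan a percentage whose denominator can be negative, near zero or zero, and whose mean, SD, minimum and maximum cannot be relied on. The algebra needs only the double-angle form. The simulated ranges rest on assumed axis distributions and SDs and show scale only; they do not predict this trial's table.

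The documents do not support an inference that effectiveness conclusions are at risk. The co-primary endpoints, power and type I error are untouched, and the damage is confined to one descriptive column.

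**What to change.** In SAP 8.4.4 item 4 and Protocol 9.11 item 4, remove percentage change for the components and report the component change in diopters (mean vector and SD).

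If a relative figure is wanted, define it as percentage change in keratometric cylinder magnitude, and restrict it to eyes with preoperative cylinder of at least 0.75 D. The restriction should be written out, because eligibility does not guarantee it in the analysis set. All-implanted does not require that eyes met the criteria, and the cylinder categories in SAP 8.1 start at 0 to 0.25 D. The table should also note that magnitude ignores rotation of the axis and tends to rise under random change. In the check above, the arm mean lay above zero in the SD 0.4 D case although the true mean vector change was zero.

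The cost is one clause in each document and the loss or redefinition of one table column. No new data are needed.
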